2.2 Prior chemoprevention studies

There have been a limited number of phase 2 chemoprevention studies in lung cancer. Among them were the Iloprost and Celecoxib trials. We participated in the multicenter double-blind, randomized, placebo-controlled phase 2 trial of oral iloprost, a prostacyclin analogue, in current and former smokers with sputum cytological atypia or endobronchial dysplasia (22). Bronchoscopy was performed at study entry and after completion of the six-months treatment. Within each subject, we calculated the average histological score of all biopsies, the worst biopsy score, and the dysplasia index. Compared with former smokers in the placebo group, former smokers treated with oral iloprost exhibited a significantly greater improvement in average score (0.41 units better, $P = 0.010$), in the worst biopsy score (1.10 units better, $P = 0.002$), and in the dysplasia index (-12.5%, 95% CI -21.0% to -3.9%, $P = 0.006$). The 6-month treatment with iloprost did not show any improvement of histological scores in current smokers (22). Endobronchial dysplasia is a presumed precursor of non-small cell lung cancer (NSCLC). In a follow-up study of a high-risk cohort of subjects with endoscopic biopsies, persistence of bronchial dysplasia was associated significantly with a 7-fold increased risk of developing NSCLC (adjusted hazard ratio = 7.8, 95% CI 1.6-39.4). Furthermore, elevated Ki-67 LI at baseline endobronchial biopsies were associated significantly with increased bronchial dysplasia score, which predates the development of lung cancer (18).

Another similar phase 2 clinical trial was the celecoxib trial conducted by Mao and colleagues (23). The study enrolled former smokers (age ≥ 45 years, ≥ 30 pack-years of smoking, ≥ 1 year of sustained abstinence from smoking) to evaluate the impact of COX-2 selective inhibitor celecoxib on cellular and molecular events associated with lung cancer pathogenesis. The primary endpoint was bronchial Ki-67 LI after 6 month treatment. Celecoxib significantly reduced Ki-67 LI by an average of 34% ($P = 0.04$). Furthermore the decrease in Ki-67 LI correlated with a reduction and/or resolution of lung nodules on CT ($P = 0.008$).

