Trace	22	663	2.58 (1.43-4.66)
Mild	37	493	5.04 (2.94-8.62)
Moderate/severe	16	315	3.20 (1.65-6.23)
P for trend			<0.0001

* Adjusted for age, sex, years of cigarette smoking, and number of cigarettes per day.

The presence of mild, moderate or severe radiographic emphysema on the LDCT scans at baseline was significantly associated with a 3- to 5-fold increased risk of developing lung cancer compared to smokers without emphysema (61).

We will recruit subjects for the present study from the existing PluSS participants who had mild, moderate or severe emphysema or GOLD II-IV COPD. Among the original PluSS participants who, as of 12/31/2015, were <75 years old, alive, free of cancer, and had quit smoking within the past 15 years, 356 had GOLD II-IV COPD (with or without emphysema), and additional 167 with mild, moderate or severe emphysema (without COPD). All these 523 subjects are potentially eligible for the proposed study. Based on our previous experience in the Iloprost study (22), which used a very similar protocol as the one proposed here, there was a 20% recruitment rate. Thus, we expect to fulfill our recruitment goal of at least 72 former smokers into the study within the first 3 years of the proposed study. With a 20% dropout rate based on our previous experience (22), we expect to have 60 study subjects who will complete the entire course of the trial.

If the proposed chemopreventive agent is effective, it will bring beneficial effect for study participants on reducing their risk of lung cancer. After the end of the study, all study participants can conduct their oral intake of Avmacol® since this dietary supplement is relatively cheap and commercially available.

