9. STATISTICAL AND SAMPLE SIZE CONSIDERATIONS

This is a randomized, double blind, placebo-controlled study to evaluate the efficacy of SF as a chemopreventive agent. Eligible subjects are former smokers with ≥ 30 pack-years smoking history who quit smoking < 15 years, and are considered at high risk for developing lung cancer. The proposed duration of therapy will be 12 months for each subject. The primary objective of this trial is to assess whether oral SF supplementation elicits an increased histologic response when compared to placebo in this population over a 12-month treatment period. The planned sample size is 72 subjects (36 per treatment arm). A block randomization scheme will be used to ensure that both treatment and placebo group have the same proportion of men and women, respectively. The randomization will be done at the UPMC Hillman Cancer Center.

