Sample size consideration. In the iloprost trial, 57 former smokers were randomized to receive oral iloprost or placebo for 6 months. Treatment effects (adjusted for baseline levels) were statistically significant ($P \leq 0.01$) for all 3 endpoints (dysplasia index, average dysplasia score, worst dysplasia score). Anticipating a 20% dropout rate over 12 months, we will randomize at least 72 study subjects to ensure that 60 subjects complete our SF study. Assuming an average baseline dysplasia index of 22% and post-therapy 11% for subjects receiving SF, a simulation with 10,000 trials with a sample size of 60 subjects has yielded an 80% statistical power to detect a statistically significant (two-sided $p < 0.05$) treatment effect, using generalized linear models (binomial family, 6 biopsies) after controlling for baseline levels of DI. Calculations are similar for other endpoints, and actual power should be greater than the DI measure because they are continuous measures and have observed within-subject correlation (i.e., repeated measures).

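### The 20% dropout is carried over from a trial with 6 months of treatment to a 12-month trial, and on that rate 72 randomised give at most about 57.6 completers, not 60.

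*Combined protocol and SAP*

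**What the plan says.** The sample size paragraph of section 9.1 plans as follows: "Anticipating a 20% dropout rate over 12 months, we will randomize at least 72 study subjects" and gives the purpose as "to ensure that 60 subjects complete our SF study". Section 9 fixes the size: "The planned sample size is 72 subjects (36 per treatment arm". It also fixes the treatment period: "The proposed duration of therapy will be 12 months for each subject".

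Section 4.2 names the source of the rate: "With a 20% dropout rate based on our previous experience (22), we expect to have 60 study subjects". Reference 22 is the oral iloprost trial, of which section 4.2 says "which used a very similar protocol as the one proposed here". On that trial's duration, section 2.2 says "Bronchoscopy was performed at study entry and after completion of the six-months treatment", and section 9.1 says "57 former smokers were randomized to receive oral iloprost or placebo for 6 months".

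Three sets of power figures rest on 60 completers: 80% for DI (section 9.1), 84% for Ki-67 (section 9.2), and 85%, 96% and 99% for gene expression at 30 per group (section 9.3). The adverse event power in section 9.4 uses all 72 subjects and is not affected.

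**The concern.** The rate is borrowed from a trial in which the second bronchoscopy came after 6 months of treatment. Here it comes after 12. Neither section 4.2 nor section 9.1 adjusts the rate or says why it should hold over twice the time. The similarity claimed for the iloprost protocol does not cover this, because treatment length is a plain difference between the two trials.

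The primary comparison needs the post-treatment biopsies, so its power depends on how many subjects reach the second bronchoscopy. If fewer than 60 do, the stated powers describe a larger trial than the one planned, and a null result could be taken as stronger evidence against an effect than it is.

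**Working it through.** **Inputs from the documents.** 72 randomised 1:1; 20% dropout; 60 completers; DI 22% at baseline and 11% after treatment on sulforaphane; 6 biopsies per subject; two-sided 0.05; stated DI power 80% (sections 9 and 9.1). Ki-67 log-scale variance 0.3480; median 10.7% falling to 6.7%, also described as a 37% reduction; stated power 84% (section 9.2).

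**Assumptions added.** The placebo DI stays at 22%, and biopsies within a subject are independent. Neither is stated; together they reproduce the plan's figure.

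**Step 1: reproduce the stated powers at 60 completers.**
- DI: two proportions, 0.22 against 0.11, with 30 x 6 = 180 biopsies per arm, gives 80.5%. A simulated binomial regression adjusted for baseline DI gives 79.4%. Stated: 80%.
- Ki-67: two-sample t-test, 30 per arm, SD = sqrt(0.3480) = 0.590. With difference ln(10.7/6.7) = 0.468, power is 85.6%; with ln(1/0.63) = 0.462, it is 84.7%. Stated: 84%.

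Both stated figures are therefore sound for 60 completers.

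**Step 2: does 72 at 20% give 60?**
- 72 x (1 - 0.20) = 57.6.
- 1 - 60/72 = 16.7%, the loss that 60 completers would imply.
- 60 x 1.20 = 72, whereas 60/0.80 = 75. The planned 72 matches multiplication by 1.20, which does not recover 60 after a 20% loss.

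**Step 3: the time base.** Cumulative dropout at month 12 is at least that at month 6. If the iloprost rate applies here, 12-month loss is 20% or more and completers are 57.6 or fewer. The documents give no dropout timing and no 12-month rate, so every value above 20% is an assumption. A constant rate over both half-years gives 1 - 0.80^2 = 36%.

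**Step 4: power over an assumed range.** Two methods are used. The direct one repeats step 1 with fewer subjects. The other scales the plan's own stated power: Phi((1.96 + z) x sqrt(n/60) - 1.96), where z = 0.842 for 80% and 0.994 for 84%. For example, DI at n = 57.6: 2.802 x 0.980 - 1.96 = 0.785, so power is 78.4%.

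| 12-month loss | Completers of 72 | DI, scaled / direct | Ki-67, scaled / direct (0.468) |
|---|---|---|---|
| 20% (no loss after month 6) | 57.6 | 78.4% / 78.9% | 82.5% / 84.1% |
| 25% (assumed) | 54.0 | 75.7% / 76.3% | 80.0% / 81.6% |
| 30% (assumed) | 50.4 | 72.8% / 73.4% | 77.3% / 78.8% |
| 36% (constant rate, illustrative) | 46.1 | 69.0% / 69.5% | 73.5% / 75.0% |

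At 23 per arm the simulated binomial regression gives 68.5% for DI. The gene-expression powers were not recomputed.

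**The case against.** The strongest reply is that the documents do not show a material loss of power. They do not say when subjects left the iloprost trial. Some loss may be a one-off refusal of the second bronchoscopy, which need not double with duration. The 36% is one convention, not a documented bound. Another source points lower: section 2.1 mentions 283 subjects in the 12-week sulforaphane beverage trial and section 4.1.6.2 reports 267 completing. If 283 is the number enrolled, loss is 16/283 = 5.7% in 12 weeks; at a constant rate that is 1 - (267/283)^(52/12), about 22% at 12 months, or about 56 completers. Those were healthy volunteers, so this is only illustrative. Section 3.5 also pays for each bronchoscopy and adds a completion bonus. Finally, 72 is worded as a minimum in sections 4.2 and 9.1, and 523 x 20% is about 105 possible recruits.

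Most of this stands. A reader might infer from the duration mismatch that the primary endpoint really has about 69% power, or that the withdrawal rules in sections 5.3.4 and 5.6 make heavy late loss likely. The documents support neither: they attach no rates to those rules, and section 5.3.4 does not expect clinically significant toxicity.

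Two things remain. The plan uses neither the payments nor the beverage trial to justify its rate. And none of these arguments turns 20% of 72 into a loss of 12; sections 1.1.1, 3 and 9 plan for 72 without the minimum wording.

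**Conclusion.** The point holds, with a small certain effect and a conditional larger one. The 20% comes from a trial with 6 months of treatment and is used for 12 months unexplained. On that rate 60 completers is too high in every case; the most is 57.6. The certain cost is one to two points of DI power (about 78-79% against 80%) and at most about two points for Ki-67 (about 82-84% against 84%). That part comes from 72 x 0.80, not from the time base.

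The time base matters only if loss continues after month 6. DI power is then about 76% at 25% loss, 73% at 30% and 69% at 36%; Ki-67 power is about 80-82%, 77-79% and 74-75%. These rest on assumed loss rates, a placebo DI that stays at 22%, and independent biopsies. It would go too far to say that the powers are materially overstated because of the duration mismatch. No size can be put on the gene-expression figures until they are rerun.

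**What to change.** In sections 4.2 and 9.1:

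- Say that the 20% comes from a trial with 6 months of treatment.
- Replace 60 completers by about 57 at 20% loss.
- Either justify a 12-month dropout rate, for instance from the timing of losses in the iloprost trial if the investigators hold it, or show a range labelled as assumed, such as 20-36% (about 57 down to 46 completers).
- Restate the DI and Ki-67 powers over that range, and rerun the gene-expression power in section 9.3 at the same completer numbers.

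The cost is wording and a rerun of existing calculations. No extra enrolment is needed. The downside is that the stated powers become less favourable.

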9.2 Statistical Analysis for Cellular Proliferation/Apoptosis Markers

Ki-67, caspase-3 and TUNEL will be quantified as % positive cells in two slides of each tissue block. First we calculate the average values of each of the 3 IHC markers over 6 tissue blocks within each bronchoscopy per patient separately for pre- and post-treatment. As described above for bronchial dysplasia measures, the primary analysis for these continuous measures will be a linear regression predicting post-treatment score by treatment group, controlling for pre-treatment score. We hypothesize that SF treated subjects will exhibit lower expression of Ki-67 and higher expression of caspase-3 and TUNEL relative to subjects in the placebo arm.

Sample Size Consideration. Using estimates of the mean and standard deviation (12.7 ± 8.2) of Ki-67 LI in the para-basal layer of bronchial epithelia of smokers (15) and the logit function, we back calculated plausible estimates of the mean (2.3676) and

variance (0.3480) of log-transformed baseline Ki-67 LI (81). Assuming these log-transformed Ki-67 LI values are normally distributed, we simulated 10,000 sets of data (n=60 each) and found an 84% statistical power with a two-sided $P<0.05$ to detect a treatment effect size of 37% for change in Ki-67 LI after 12 months of SF treatment (i.e., median Ki-67 LI of 10.7% at baseline and 6.7% at follow-up on SF). This detectable effect size is smaller than 61% reduction in cell proliferation marker in the SF treatment group (14). Furthermore, a recent randomized, double-blind, placebo-controlled phase 2 clinical trial involving 58 women found that oral intake of SF glucosinolate for 2-8 weeks resulted in a statistically significant reduction of mean Ki-67 LI ($P = 0.01$) (16).

9.3 Statistical Analysis for Gene Expression

A summary gene expression score will be derived from previously determined gene expression features of 23 genes (19,82): $\text{score} = e^y / (1 + e^y)$, where $y = b_0 + \sum b_j * x_j$, where b_0 is the intercept, b_j is the coefficient, and x_j is the feature of the gene j expression [see details in (82)]. We will calculate the gene expression score (0~1) for each subject pre and post treatment separately. A linear mixed effect model will be used to assess the effect of SF on post-treatment gene expression scores, similar as described in Section 4.2.1. A decreased gene expression score post-treatment towards those seen in bronchial benign disease is indicative of the chemopreventive effect of SF on the lung cancer-gene expression.

We will use the similar approach to calculate a summary gene expression score of the 280-gene signature in bronchial premalignant lesions (PMLs) in identified our preliminary study. Similarly a linear mixed effect model will be used to assess the post-treatment gene expression scores. If SF causes a significant change of the score towards the regression of PMLs based on histological dysplasia index score, the gene-level expression changes will be examined to estimate the SF-treatment effects on individual gene or a cluster of genes.

To assess the similarity and difference in the gene expressions between the bronchial airway and nasal epithelia, we will use our similar methodologies described previously (73). For each gene identified in the analysis above, we will use a linear mixed effects model that includes site (bronchus or nose) and treatment (SF or placebo) as fixed effect. The regression model is given: $G_{ij} \sim \mu + \beta_s \cdot X_s + \beta_t \cdot X_t + \beta_{st} \cdot X_s \cdot X_t + \varepsilon_{ij}$, where G_{ij} is the \log_2 expression value for gene i in patient j ; the parameter μ is the overall mean of \log_2 fold change in gene expression, β_s and β_t for the respective site- and treatment-specific effect, and β_{st} for the interaction between site and treatment; and X_s for site (1=nose, 0=bronchus) and X_t for treatment (1=SF, 0=placebo).

Sample Size Consideration. The Affymetrix Human Gene 1.0 ST Array contains ~36,000 gene transcripts. The proposed study with 30 subjects per group will have a 85% power to detect a 2-fold gene expression difference pre and post treatment ($\log_2 |d|=1.0$, $\sigma_d = 0.7$) for 23 identified cancer-related genes at a false discovery rate (FDR)<0.05 using the method of Liu and Hwang (83), assuming 99.9% non-differentially expressed genes ($\pi_0 = 0.999$). Similarly the study will have a 96% power for 280 PMLs-related genes (i.e., $\pi_0 = 0.990$), and a 99% power for 5% differentially expressed genes (i.e., $\pi_0 = 0.950$) in exploratory analysis.

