1.2 Secondary Aims

- 1.2.1 To explore if daily oral dose of 120 micromole SF for 12 months can modulate the changes of the lung cancer-related gene expression markers in bronchial epithelia in former smokers at high risk for lung cancer.
- 1.2.2 To explore if daily oral dose of 120 micromole SF for 12 months can modulate the changes of bronchial premalignant lesions-related gene expression markers in former smokers at high risk for lung cancer.
- 1.2.3 To explore if daily oral dose of 120 micromole SF for 12 months can modulate the similar changes of the gene expression markers in nasal epithelia as in the bronchial epithelia identified in Aims 1.2.1 and 1.2.2.

- 1.1.4 To determine the safety and toxicity of daily oral dose of 120 micromole SF for 12 months in former smokers at high risk for lung cancer.

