The unified airway field of injury concept suggests that cigarette smoking renders injury throughout the entire respiratory tract. Studies have shown that tobacco-related gene expression alterations in the extra-thoracic epithelium of the nose and mouth similarly reflect the host response to cigarette smoke in the distal airway (79). Both nasal and bronchial epithelial cells demonstrate similar patterns of gene expression changes in response to cigarette smoking (73), suggesting that the nasal epithelium may be a surrogate biospecimen for monitoring the individual response to smoking and potentially the risk for lung cancer. More recently, we have demonstrated that the cancer-specific gene-expression changes in the bronchial epithelium are enriched among gene-expression alterations observed in the nasal epithelium from approximately 500 smokers with matched nasal and bronchial samples. These data suggest that genomic profiling of these relatively accessible airway cells may be an intermediate endpoint of chemoprevention for lung cancer. In the proposed study, we will explore whether SF-induced gene expression changes in bronchial epithelium mirror those in the nasal epithelium.

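### The nose-bronchus comparison appears to be limited to genes picked for their bronchial response in the same patients, which biases it against the nose when sulforaphane effects are small or sparse

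*Combined protocol and SAP*

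**What the plan says.** Aim 1.2.3 (section 1.2) asks whether SF "can modulate the similar changes of the gene expression markers in nasal epithelia as in the bronchial epithelia identified in Aims 1.2.1 and 1.2.2". Section 8.2.4 puts the question as: "we will explore whether SF-induced gene expression changes in bronchial epithelium mirror those in the nasal epithelium".

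For the 280-gene panel, section 9.3 makes the gene-level work conditional: "If SF causes a significant change of the score towards the regression of PMLs based on histological dysplasia index score", then "the gene-level expression changes will be examined to estimate the SF-treatment effects on individual gene or a cluster of genes". No gene-level threshold is given. The 23-gene paragraph describes a summary score and no gene-level step.

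The site comparison follows. Its purpose is "To assess the similarity and difference in the gene expressions between the bronchial airway and nasal epithelia", and the model is introduced with "For each gene identified in the analysis above, we will use a linear mixed effects model that includes site (bronchus or nose". Treatment is the other fixed effect, and a coefficient is included "for the interaction between site and treatment". No test level, margin, concordance measure or decision rule is attached to that coefficient. The methods are said to resemble those of an earlier publication.

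Bronchial brushings are taken before and after treatment (section 8.1.2) and nasal brushings at months 0, 3, 6, 9 and 12 (section 8.1.4), in the same patients.

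**The concern.** If a gene enters the site model because its bronchial SF effect looked large in this trial, its bronchial estimate is on average too high. The nasal estimate shares that error only as far as the two sites are correlated. The interaction then starts from a gap that selection has created. A patient term or baseline adjustment does not remove it, because the problem is which genes are looked at.

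Section 8.2.4 presents nasal epithelium as a possible surrogate specimen. A spurious shortfall in the nose would count against it. The stated goal includes similarity, yet the text gives no measure by which similarity could be shown.

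**Working it through.** **Inputs from section 9.3 (sample size paragraph).** 30 subjects per group, SD 0.7 on the log2 scale, design effect 1.0 log2, FDR 0.05.

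**Assumed, not in the documents.** Equal SD at both sites, analysis of change, independent genes, nose-bronchus correlation ρ of 0, 0.3 or 0.6.

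**The plan's own figure.** Using the Liu-Hwang method with a two-sample t-test on 58 df, the SE is 0.7 × √(2/30) = 0.181 and the noncentrality is 1/0.181 = 5.53. The critical value is where P(reject | null)/P(reject | effect) = (0.05/0.95) × (1 − π0)/π0. Power comes out at 85.4%, 96.1% and 99.0% for π0 = 0.999, 0.990 and 0.950, against the stated 85%, 96% and 99%. So the plan's SE is 0.181. At π0 = 0.999 the implied p-value threshold is (0.05/0.95) × (0.001/0.999) × 0.854 = 4.5 × 10⁻⁵.

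**Mechanism.** With equal true effects and equal SDs:
- mean nasal estimate after selection = true + ρ × (mean bronchial estimate − true)
- selection gap = (1 − ρ) × (bronchial inflation)
- interaction SE = 0.181 × √(2(1 − ρ)) = 0.256, 0.214 and 0.162 for ρ = 0, 0.3 and 0.6

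With FDR selection among 280 genes, a gene passing alone needs p ≤ 0.05/280 = 0.00018, so |z| ≥ about 3.75 and an estimate of about 3.75 × 0.181 = 0.68 log2. A gene with a true effect of 0.2 gets in only if overestimated more than threefold.

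**Simulated false interaction rates (nominal 5%), true effects equal at both sites.** Where one figure is given, it is for ρ = 0.3.

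| True SF effect | Selection on bronchus | Bronchus v nose at ρ = 0.3 (log2) | False interactions |
|---|---|---|---|
| Spread over genes, SD 0.2 | FDR 0.05, 280 genes | 0.65 v 0.44 | about 10-18% (ρ 0.6 to 0) |
| 0.2 in every gene | FDR 0.05, 280 genes | about 0.65 v 0.33 | about 18-40% (ρ 0.6 to 0) |
| 0.5, sparse | p < 4.5 × 10⁻⁵ | 0.83 v 0.60 | 11-21% (ρ 0.6 to 0) |
| 0.5 in every gene | FDR 0.05, 280 genes | 0.58 v 0.52 | about 4% |
| 1.0 | p < 4.5 × 10⁻⁵ | 1.04 v 1.01 | 3.9-4.5% (ρ 0 to 0.6) |
| 0 to 1.0 | none, all genes tested | no selection gap | 4.9-5.1% |

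Check of the third row: 0.5 + 0.3 × (0.83 − 0.5) = 0.60. The gap of 0.23 is 0.23/0.214 = 1.1 interaction standard errors.

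The first two rows treat the SE as known. In the second row about 4 of 280 genes are selected per trial on average, or nearer 1.5 with a t reference, so the high rate applies to very few genes.

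**What a non-significant interaction can show.** Without selection, if the nose carries half the bronchial effect, the interaction is non-significant in 51%, 37% and 14% of genes at 1.0 v 0.5 log2 (ρ = 0, 0.3, 0.6). At 0.5 v 0.25 log2 it is 84%, 79% and 67%.

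**Whether a slope across genes would serve instead.** The slope of estimated nasal on estimated bronchial effects tends to (τ² + ρ × SE²)/(τ² + SE²), where τ is the SD of true effects between genes. With identical true effects at the two sites, τ = 0.2 and ρ = 0.3, this is (0.0400 + 0.3 × 0.0327)/(0.0400 + 0.0327) = 0.69, not 1. With no SF effect at either site (τ = 0) it equals ρ, which is false similarity. Resampling patients gives a CI around the biased value and does not correct it.

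**The case against.** The strongest reply is that selection on trial results is not stated. Section 8.2.4 and the sample size paragraph of section 9.3 both use the word *identified* for the fixed 280- and 23-gene panels, which were derived outside this trial. The written gate is a summary score, and the gene-level step only estimates effects. If the panels are meant, all panel genes enter and there is no selection bias. That reading is possible. Aim 1.2.3, which ties the nasal question to bronchial changes identified under the two preceding aims, makes the other more natural.

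Three stronger readings are tempting and should not be drawn:

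- **That the plan builds in a false site difference in general.** It does not. At the 1.0 log2 design effect the gap is at most 0.045 log2. At 0.5 log2 in all genes there is no excess of false interactions. Null genes picked at an unadjusted p < 0.05 would look far worse, but the only gene-level criterion in the documents is FDR < 0.05, which seldom admits any gene when all are null.
- **That a non-significant interaction will be read as similarity.** No text says so. What can be said is that section 9.3 states no similarity criterion; the publication it refers to may contain one.
- **That this analysis decides whether nasal brushing replaces bronchoscopy.** The aim is secondary and worded as exploratory, and the primary endpoint needs biopsies.

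It can also be argued that with no bronchial change there is nothing to mirror, so the score gate does little harm. That is fair if the effect is truly absent, less so if the score merely misses significance.

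**Conclusion.** The point holds in limited form. On the natural reading of Aim 1.2.3 and section 9.3, bronchial data both select the genes and supply one side of the contrast. When SF effects are small or sparse, false site differences rise from 5% to about 10-18% (effects spread with SD 0.2) or about 18-40% (uniform 0.2 log2, few genes selected), always towards a weaker nasal response. At the design effect the distortion is negligible. On the fixed-panel reading it is absent, and only the wording needs changing.

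These sizes rest on the plan's 30 per arm and SD 0.7 and on the assumptions listed above. The extra conditioning from the score gate was not modelled. The lack of a similarity criterion stands under either reading, subject to what the cited methods contain.

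**What to change.** In section 9.3, state that the site-by-treatment model is fitted to all 23 and all 280 prespecified genes, whatever their bronchial result and whether or not the score change is significant. In the simulations this restores the 5% rate. If the fixed panels were always intended, the same sentence settles the ambiguity.

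For each gene, report the SF v placebo effect in nasal samples and the interaction estimate with its CI. State that a non-significant interaction is not evidence of similarity. Do not adopt a naive slope or correlation of estimated nasal on estimated bronchial effects as the similarity criterion, because sampling error and shared-patient noise bias it.

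The cost is a few sentences of SAP text, a larger multiplicity set and a little more analysis. The brushings are already planned, so no new samples are needed.
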